- Higher body weights are expected for this population compared to the psoriasis population (approximately 10 kg heavier weight for HS population in clinical trials ([Kimball et al 2016](#))), thus potentially requiring higher doses to achieve adequate exposure. Secukinumab systemic exposure varies with body weight in an allometric relationship. For clearance, the allometric exponent was estimated to be close to 1; in other words, a doubling of body weight could lead to a nearly 2-fold increase in clearance and therefore reduced serum exposure ([Bruin et al 2017](#)). Therefore, evaluation of a dosing regimen with higher exposure than that resulting from the marketed regimen is appropriate in this heavier patient population.
- Higher local exposure than in psoriasis might be needed for this disease with deep inflammatory subcutaneous lesions.
- Clinical experience with adalimumab in HS supports a dosing regimen with higher exposure in HS than in psoriasis.

After the same induction period during the first month, considerably higher and more consistent systemic exposure can be achieved with a shortened dose interval (every 2 weeks) than can be reached with the 4 weeks interval ([Figure 4-1](#)).

Secukinumab 300 mg s.c. every 2 weeks has been tested in over 300 patients for at least 24 weeks in completed clinical studies in uveitis and psoriasis. A safety profile in line with that of secukinumab 300 mg s.c. every 4 weeks has been observed.

Figure 4-1 Predicted systemic exposure with 2 and 4 weeks dosing intervals during maintenance at the 300 mg dose level

[figure not shown]

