6.3.2 Treatment assignment, randomization

The investigator or his/her delegate will contact the IRT after confirming that the subject fulfills all the inclusion/exclusion criteria. The IRT will assign a randomization number to the subject, which will be used to link the subject to a treatment arm and will specify a unique medication number for the package of study drug to be dispensed to the subject. The randomization number will not be communicated to the investigator or his/her delegate.

The randomization numbers will be generated using the following procedure to ensure that treatment assignment is unbiased and concealed from subjects and investigator staff. A patient randomization list will be produced by the IRT provider using a validated system that automates the random assignment of patient numbers to randomization numbers. These randomization numbers are linked to the different treatment arms, which in turn are linked to medication numbers. A separate medication list will be produced by or under the responsibility of Novartis Clinical Drug Supply using a validated system that automates the random assignment of medication numbers to packs containing the investigational drug(s).

Randomization will be stratified by region, concomitant antibiotic use (Yes/No) and body weight (weight < 90kg / ≥ 90kg).

The randomization scheme for subjects will be reviewed and approved by a member of the Randomization Group.

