12.4.2 Statistical model, hypothesis, and method of analysis

The statistical hypotheses for the primary endpoint being tested is that there is no difference in the proportion of HiSCR at Week 16 in any of the secukinumab regimens versus placebo regimen.

Let p_j denote the proportion of HiSCR at Week 16 for treatment regimens j , $j = 0, 1, 2$ where

- 0 corresponds to placebo regimen,
- 1 corresponds to secukinumab 300 mg q2w s.c.,
- 2 corresponds to secukinumab 300 mg q4w s.c.,

In statistical terms, $H_j: p_j = p_0, H_{A_j}: p_j \neq p_0$ for the j th secukinumab regimen, i.e.

H_1 : secukinumab 300 mg q2w s.c. is not different to placebo regimen with respect to HiSCR after 16 weeks of treatment.

H_2 : secukinumab 300 mg q4w s.c. is not different to placebo regimen with respect to HiSCR after 16 weeks of treatment.

The primary analysis method will be logistic regression with treatment group, geographical region, Hurley stage, use of antibiotic, baseline body weight and baseline AN counts as explanatory variables. Odds ratios will be computed for comparisons of secukinumab dose regimens versus placebo utilizing the logistic regression model fitted. In case of response rates of 0% or of 100% in one of the treatment groups, Fisher's exact test will be applied. Risk difference and confidence intervals for risk difference will be provided.

The detailed testing strategy including the primary endpoint analysis is provided in [Section 12.5](#). Efficacy of two secukinumab regimens compared to placebo with respect to HiSCR after 16 weeks of treatment could be demonstrated if H_1 and/or H_2 is/are rejected and the treatment effect is in favor of secukinumab.

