12.5 Analysis of secondary endpoints

12.5.1 Efficacy and/or Pharmacodynamic endpoint(s)

The secondary endpoints of this study are planned as follow:

- Percentage change from baseline in AN count at Week 16
- Flare over 16 weeks: Patients who experience at least one flare over 16 weeks. Flare is defined as an at least a 25% increase in AN counts with a minimum increase of 2 AN relative to baseline.
- Pain/NSR30 at Week 16: Patients achieving NRS30 at Week 16, among patients with baseline NRS \geq 3. NRS30 is defined as at least 30% reduction and at least 2 unit reduction from baseline in Patient's Global Assessment of Skin Pain. NRS from baseline to Week 16 is the weekly average score calculated based on the 7 available daily scores: Baseline (Week 0) will be average of NRS score from day -7 to day -1, week 1 will be average of

score from day 1 to day 7, week 2 will be average of score from day 8 to day 14 and so on. For any week with less than 4 diary entries within the week, the weekly average will be recorded as missing.

For the secondary endpoint of percentage change in AN count from baseline to Week 16, an analysis of covariance (ANCOVA) model will be fitted to estimate the treatment differences between the two secukinumab regimens and placebo with treatment group, baseline AN count, Hurley stage, use of antibiotic, geographical region and baseline body weight as covariates.

The analysis method for both flare up to Week 16 and Pain/NRS30 at Week 16 will be the logistic regression: with treatment group, Hurley stage, geographical region, use of antibiotic, baseline body weight and baseline AN counts as explanatory variables for flare endpoints; and with treatment group, Hurley stage, region, use of antibiotic, baseline body weight and baseline NRS as explanatory variables for pain endpoints. Odds ratios will be computed for comparisons of secukinumab dose regimens versus placebo utilizing the logistic regression model fitted. In case of response rates of 0% or of 100% in one of the treatment groups, Fisher's exact test will be applied. Risk difference and confidence intervals for risk difference will be provided.

Testing strategy

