12.5.6 PK/PD relationships

The effect of the secukinumab serum concentration on HiSCR and other endpoints will be investigated if appropriate. Clinically important subject covariates, such as Hurley stage, geographical region, use of antibiotic, baseline body weight, age and baseline AN count will be investigated.

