### 1.1 Study design

This is a multicenter, randomized, double-blind, placebo controlled, parallel group study with two secukinumab dose regimens planned in approximately 541 subjects with moderate to severe hidradenitis suppurativa (HS).

The study consists of: Screening (up to 4 weeks), Treatment Period 1 (16 weeks) and Treatment Period 2 (36 weeks; optionally extended up to 48 weeks in case of pandemic major disruptions). Subjects who prematurely discontinue the study, or who complete the study and do not wish to continue in an optional extension study, will need to complete a post-treatment Follow-Up period (8 weeks).

Subjects will be randomized at a 1:1:0.5:0.5 ratio to one of four treatment arms at the time of randomization (baseline) visit:

- Secukinumab 300 mg every 2 weeks
- Secukinumab 300 mg every 4 weeks
- Placebo to secukinumab 300 mg every 2 weeks
- Placebo to secukinumab 300 mg every 4 weeks

Approximately 180 subjects are planned to be randomized to each of the two secukinumab arms and another approximately 180 subjects are planned to be randomized to the two placebo to secukinumab arms. Randomization will be stratified by region, current antibiotic use and body weight.

Subjects who complete Treatment Period 1 will enter Treatment Period 2. At Week 16, subjects who were randomized to one of the two secukinumab arms will continue on the same dose. Subjects who were randomized to the two placebo to secukinumab arms will start either

[figure not shown]
secukinumab 300 mg every 4 weeks or secukinumab 300 mg every 2 weeks according to their treatment arms definition.

The planned end of Treatment Period 2 visit (EOT 2) will be performed at Week 52. At this visit, the site should call Interactive Response Technology (IRT) after performing the scheduled study assessments to record the completion of the Treatment Period for the subject(s). For subjects rolling over to the optional extension study, Week 52 will be the end of study visit; for subjects continuing to the post-treatment Follow-Up period, the visit at Week 60 will be the end of study visit.

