- A mixed effects logistic regression model (MELRM) will be fitted. The endpoint is HiSCR at all time points from Week 2 up to Week 52 and are included on the left hand side of the model as dependent variables. The covariates included as fixed effects are: treatment group, visit, baseline AN count and the interaction between visit and treatment group. An unstructured covariance structure will be applied. In case of non-convergence, alternative covariance structures will be considered. If additional convergence issues are encountered, then modifications to the model will be considered.

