#### 5.4.2.2 Mixed effects logistic regression model (MELRM)

A mixed effects logistic regression model will be fitted. The endpoint is binary and all time points from week 2 up to week 52 are included on the left hand side of the model as dependent variables. The covariates included as fixed effects are: treatment group, visit, baseline AN count (or NRS for Skin Pain/NRS30) and the interaction between visit and treatment group. An unstructured covariance structure will be applied. In case of non-convergence, alternative covariance structures will be considered. If additional convergence issues are encountered, then modifications to the model will be considered.

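### The SAP's exploratory models up to Week 52 omit region, antibiotic use, body weight and Hurley stage without a stated reason; if these factors are prognostic, adding them brings a small gain

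*SAP*

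**What the plan says.** SAP 2.13 fits five models to data from Week 2 to Week 52: mixed effects logistic models (MELRM) for HiSCR, AN50, flare and NRS30, and an MMRM for percentage change in AN count. For HiSCR: "The covariates included as fixed effects are: treatment group, visit, baseline AN count and the interaction between visit and treatment group". SAP 5.4.1.1 repeats that list for the MMRM. SAP 5.4.2.2 gives the general logistic form: "treatment group, visit, baseline AN count (or NRS for Skin Pain/NRS30) and the interaction between visit and treatment group". All five ask for an unstructured covariance, with other structures and then model changes if the fit does not converge.

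On allocation, Protocol 6.3.2 says "Randomization will be stratified by region, concomitant antibiotic use (Yes/No) and body weight", the weight split being below versus at or above 90 kg. SAP 1.1 agrees: "Randomization will be stratified by region, current antibiotic use and body weight". Hurley stage is not a stratification factor.

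The protocol's Week 16 models use a longer list. For HiSCR (Protocol 12.4.2): "The primary analysis method will be logistic regression with treatment group, geographical region, Hurley stage, use of antibiotic, baseline body weight and baseline AN counts". For pain (Protocol 12.5.1) the model is fitted "with treatment group, Hurley stage, region, use of antibiotic, baseline body weight and baseline NRS as explanatory variables for pain endpoints". The AN-count and flare models in the same section also have all four factors, as do the exploratory repeated-measures models for mHSS and DLQI in Protocol 12.6. SAP section 4, on changes from the protocol, mentions only the HS-PGA response definition.

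**The concern.** A model that leaves out the factors used to stratify allocation does not credit the balance that stratification produced. If those factors predict outcome, the model-based standard errors are too large. A prognostic factor that was not stratified, such as Hurley stage, also leaves real chance imbalance uncorrected.

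Exploratory status does not explain the short list, because the protocol's own exploratory MMRMs carry the four factors. Protocol 12.5.6 plans to investigate "Clinically important subject covariates, such as Hurley stage, geographical region, use of antibiotic, baseline body weight, age and baseline AN count" in the PK/PD work, and Protocol 4.2 states "Secukinumab systemic exposure varies with body weight in an allometric relationship".

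What is at stake is the precision of the long-term efficacy description, and how easily it compares with the Week 16 results.

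**Working it through.** **1. Plan figures.** The documents give no precision figure for the Week 52 models. The nearest input is the SD of 46 points for percentage change in AN count (Protocol 12.8.2). It reproduces the stated power with 471/3 = 157 per group: 18/(46·√(2/157)) = 18/5.19 = 3.467. Less 2.054 (two-sided 4%) this gives 92.1%, and less 2.576 (two-sided 1%) it gives 81.4%. The plan states 92% and 81%.

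**2. Assumptions.** The documents do not give the prognostic strength of the four factors. Let R² be the share of residual variance they explain together, taken as 2%, 5% and 10%. The simulations behind steps 4 and 5 assume 540 patients allocated 1:1:0.5:0.5 in stratified blocks of 6, 4 regions, 35% on antibiotics, 50% at or above 90 kg, and Hurley I/II/III at 10/50/40%.

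**3. AN-count MMRM, reported standard error.** Omitting the factors inflates it by about 1/√(1−R²):
- R² 2%: 1/√0.98 = 1.010
- R² 5%: 1/√0.95 = 1.026
- R² 10%: 1/√0.90 = 1.054

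After the small cost of estimating the extra coefficients, the excess is 0.8%, 2.4% and 5.2%. As an illustration (the SAP names no contrast), the difference between two arms of 180 has SE 46·√(2/180) = 4.85 without the factors, and 4.81, 4.74 and 4.61 with them. The percentages do not depend on the SD.

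**4. AN-count MMRM, real loss.** The true spread of the estimate rises only through the share h of R² that allocation does not balance, by about √(1 + h·R²/(1−R²)) − 1. With h = 0.25 and R² = 10% this is √(1 + 0.25·0.111) − 1 = 1.4%. The simulation (4,000 allocations, one visit, complete data) gave:

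| Share carried by Hurley stage | R² 2% | R² 5% | R² 10% |
|---|---|---|---|
| One quarter (equal shares) | 0.1% | 0.5% | 1.4% |
| One half | 0.3% | 1.2% | 2.7% |

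If Hurley stage carries none, the rise is at most 0.3%. With equal shares a nominal 95% interval covers 95.2%, 95.4% and 95.8%. Stratification balances only the 90 kg split, so any prognostic weight variation within a category also belongs in h.

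**5. The four MELRMs.** The SAP does not say whether the unstructured covariance applies to random effects or to residuals, and the answer depends on this. These results use 15 visits, 20% random dropout and 100 simulated trials per setting. Each row gives the effect of leaving the factors out.

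| Fit | Quantity | R² 2% | R² 5% | R² 10% |
|---|---|---|---|---|
| Random intercept | SE of log odds ratio | +0.7% | +1.6% | +3.3% |
| Random intercept | z | −1.4% | −1.6% | −3.6% |
| Marginal | log odds ratio | −2.7% | −3.1% | −7.2% |
| Marginal | robust SE | −1.0% | −2.1% | −4.0% |
| Marginal | z | −1.6% | −1.0% | −3.4% |

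In the marginal form, adding the factors therefore widens the odds ratio interval and moves the estimate further from the null. This is non-collapsibility. A separate, smaller simulation agreed in direction. Adding the factors, with a linear predictor of SD 0, 0.5 and 1.0 on the logit scale, multiplied the random-intercept SE by 1.000, 0.988 and 0.955. It multiplied the marginal SE by 1.007 and 1.017 at SD 0 and 0.5.

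**6. Size of the change.** Four groups (SAP 2.3.1) by 15 lesion-count visits (Protocol Table 8-1), plus one baseline term, gives 61 fixed effects. An unstructured 15-visit matrix has 15·16/2 = 120 parameters. The four factors add 3 + 1 + 1 + 2 = 7 (4 regions assumed, weight as one term).

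**The case against.** The strongest reply is that this is a modelling preference. The analyses are exploratory and the protocol sets no Week 52 model for these endpoints. The models are already large enough to need a written fallback, so a short list is defensible. These points stand, and they are why the point is optional. A reader might infer that the SAP departs from the protocol, or that the Week 16 tests or stated power are weakened. The documents support neither: the confirmatory analyses are in the separate Week 16 SAP.

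A second tempting reading is that adjustment would tighten every interval. It would not, as the marginal results show, and four of the five endpoints use the logistic model. The model paragraphs also name no contrast or interval as output. The score intervals for simple proportions in SAP 5.4.2.1 would not change at all.

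A third is that real precision is lost only through Hurley stage. Within-category body weight can contribute too, and dropout by Week 52 can disturb the balance set at randomisation.

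Nor do the protocol passages show that the factors are prognostic. One lists covariates to be examined, and the other concerns drug exposure. The logistic figures rest on 100 trials per setting and are noisy: the marginal z loss is 1.6% at R² 2% but 1.0% at 5%.

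What remains is an unexplained difference from the protocol's own covariate list, in the direction of standard errors that are too wide.

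**Conclusion.** The point holds as an optional improvement. All five Week 52 models omit the three stratification factors and Hurley stage, and the SAP gives no reason.

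If the four factors explain 2% to 10% of residual variance, the AN-count MMRM reports standard errors about 1% to 5% too wide. Most of that is conservatism. The real loss is about 0.1% to 1.4% with equal shares, and up to 2.7% if Hurley stage carries half; prognostic weight differences within a category could add to it. For the MELRMs the gain is a slightly narrower interval with subject random effects, and only a slightly larger z under a marginal fit. If the factors are not prognostic there is no gain.

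The sizes rest on an assumed R² and the allocation assumptions listed above.

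**What to change.** In SAP 2.13, 5.4.1.1 and 5.4.2.2, add region, antibiotic use, baseline body weight and Hurley stage as main fixed effects. Use the actual stratum where it differs from the one recorded in IRT, as SAP 2.2 already provides. State that if a MELRM still fails to converge under the existing fallback, these added covariates may be dropped.

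The cost is SAP text and model statements; all four variables are already summarised at baseline under SAP 2.4. The downside is about seven more parameters and a small convergence risk. All 1,600 test fits converged, but they used a random intercept or a marginal form. The full unstructured random-effects model over 15 visits was not tested. Under a marginal fit the reported odds ratio also becomes conditional on the added factors. If response rates are to be read from the model, the SAP would need a rule for standardising them.

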### **Percentage change from baseline in AN count**

The mean change from baseline in AN count up to Week 52 will be presented for each treatment group. Observed values will be presented.

A mixed model for repeated measures (MMRM) will be fitted. The endpoint is percentage change from baseline in AN count and all time points from Week 2 up to Week 52 are included on the left hand side of the model as dependent variables. The covariates included as fixed effects are: treatment group, visit, baseline AN count and the interaction between visit and treatment group. An unstructured covariance structure will be applied. In case of non-convergence, alternative covariance structures will be considered. If additional convergence issues are encountered, then modifications to the model will be considered.

## Achievement of AN50

The number and percentage of AN50 up to Week 52 will be presented for each treatment group. Observed values will be presented.

Figures will be provided displaying estimates for AN50 rates by treatment groups including confidence intervals.

A similar MELRM analysis as described for HiSCR will be performed for this endpoint. The endpoint is the achievement of AN50 and all time points from Week 2 up to Week 52 are included on the left hand side of the model as dependent variables. The covariates included as fixed effects are: treatment group, visit, baseline AN count and the interaction between visit and treatment group. An unstructured covariance structure will be applied. In case of non-convergence, alternative covariance structures will be considered. If additional convergence issues are encountered, then modifications to the model will be considered.

## Flare

The number and percentage of Flare up to Week 52 will be presented for each treatment group. Observed values will be presented.

Figures will be provided displaying estimates for flaring rates by treatment groups including confidence intervals.

A Kaplan-Meier (KM) analysis for the cumulative incidence of the Flare-free period up to Week 52 will be presented for each treatment group. Observed values will be presented. Patients without Flare will be censored at the last known visit. Corresponding KM figures will also be provided.

A similar MELRM analysis as described for HiSCR will be performed for this endpoint.

rom Week 2 up to Week 52 are included on the left hand side of the model as dependent variables. The covariates included as fixed effects are: treatment group, visit, baseline AN count and the interaction between visit and treatment group. An unstructured covariance structure will be applied. In case of non-convergence, alternative covariance structures will be considered. If additional convergence issues are encountered, then modifications to the model will be considered.

## Skin Pain/NRS30

The number and percentage of NRS30 responder subjects will be presented by visit up to Week 52 for each treatment group observed values will be presented.

Figures will be provided displaying estimates for responder rates by treatment groups including confidence intervals.

A similar MELRM analysis as described for HiSCR will be performed for this endpoint.

The endpoint is the achievement of NRS30 and all time points for time windows from Week 2 up to Week 52 are included on the left hand side of the model as dependent variables. The covariates included as fixed effects are: treatment group, visit, baseline NRS score and the interaction between visit and treatment group. An unstructured covariance structure will be applied. In case of non-convergence, alternative covariance structures will be considered. If

additional convergence issues are encountered, then modifications to the model will be considered.

Analyses will be performed at a study level and also pooling both studies.

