12.8.2 Secondary endpoint(s)

The power mentioned for the Secondary endpoints is conditional on the successful rejection of the null hypothesis for the primary endpoint (HiSCR), and the testing procedures are defined in [Section 12.5.1](#).

Percentage change in AN count: based on adalimumab phase III placebo-controlled studies (PIONEER I and II, respectively ([Kimball et al 2016](#))), it is assumed that the difference between secukinumab and placebo is at least 18% in favor of secukinumab when considering the mean percentage change from baseline in AN count at Week 16. Although it is planned to use a repeated measures model for the analysis, an approximate sample size can be based on a simple t-test. The original sample size of 471 patients is sufficient to achieve 92% power in secukinumab 300 mg q2w vs. placebo and 81% power in secukinumab 300 mg q4w vs. placebo when assuming a standard deviation of 46%.

Flare: Based on adalimumab phase III placebo-controlled studies (PIONEER I and II, respectively, [Kimball et al 2016](#)), a placebo rate of 35% is assumed. The original sample size

of 471 patients is sufficient to achieve 98% power for the demonstration of 20% difference of secukinumab 300 mg q2w over placebo based on the second endpoint when assuming secukinumab 300 mg q2w rate to be 15%. Assuming the same rate for secukinumab 300 mg q4w, the sample size would be sufficient to achieve 92% power in a comparison of secukinumab 300 mg q4w vs. placebo.

Pain: Based on adalimumab phase III placebo-controlled studies (PIONEER I and II, respectively, [Kimball et al 2016](#)), a placebo rate of 23% is assumed. Assuming 80% patients are qualified to calculate Pain variable NRS30, the original total sample size of 942 patients across two studies is sufficient to achieve 85% power for the demonstration of 13% difference of secukinumab 300 mg q2w over placebo based on the second endpoint when assuming the rate to be 36%. The original sample size is also sufficient to achieve 70% power to demonstrate superiority of secukinumab 300 mg q4w over placebo based on the same assumptions in regards to the rates of secukinumab and placebo as above.

13 Ethical considerations and administrative procedures

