**Table 1-1 Objective and related endpoints**

Objective(s)	Endpoint(s)
Primary objective(s)	Endpoint(s) for primary objective(s)

To demonstrate the efficacy of secukinumab compared to placebo with respect to HiSCR after 16 weeks of treatment.

	

Achievement of HiSCR at Week 16. HiSCR is defined as at least a 50% decrease in Abscess and Inflammatory Nodule (AN) count with no increase in the number of abscesses and/or in the number of draining fistulae.

Secondary objective(s)	Endpoint(s) for secondary objective(s)

To demonstrate the efficacy of secukinumab compared to placebo after 16 weeks of treatment with respect to AN count.

To demonstrate the efficacy of secukinumab compared to placebo with respect to:

proportion of subjects with HS flares

proportion of subjects with clinical response in HS related skin pain

	

Percentage change from baseline in AN count at Week 16.

Flaring up to Week 16. Flare is defined as at least a 25% increase in AN counts with a minimum increase of 2 AN relative to baseline.

Achievement of NRS30 at Week 16, among subjects with baseline NRS <math>\geq 3</math>.

Objective(s)	Endpoint(s)
	NRS30 is defined as at least a 30% reduction and at least 2 units reduction from baseline in Patient's Global Assessment of Skin Pain - at worst.
Exploratory objective(s)	Endpoint(s) for exploratory objective(s)

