

To evaluate the safety and tolerability of secukinumab over 52 weeks of treatment.

To explore the long-term effect of secukinumab with respect to HiSCR, AN count, proportion of subjects with flares, HS related skin pain up to 52 weeks of treatment.

To evaluate the effect of secukinumab with respect to the following efficacy assessments:

Modified Hidradenitis Suppurativa Score (mHSS);

HS-Physician's Global Assessment (HS-PGA);

Dermatology Life Quality Index (DLQI);

Health Status Questionnaire (EQ-5D-3L);

Patient Global Impression of severity (PGI-s);

Patient Global Impression of change (PGI-c);

Work Productivity Activity Impairment (WPAI);

HS Symptom Diary

Inflammatory markers with respect to CRP and ESR compared to placebo after 16 weeks and in the two secukinumab dose regimens up to 52 weeks of treatment.

	

Clinical safety and tolerability assessments:

physical exams,

vital signs,

laboratory assessments,

AE monitoring

Achievement of clinical response as defined by HiSCR, HiSCR25, HiSCR50, HiSCR75, HiSCR90, HiSCR100.

Absolute/percent and percentage change from baseline in AN count, AN (0/1), AN25, AN 50, AN75, AN90, AN100 response.

Flares.

Achievement of pain relief as defined by NRS30.

Absolute and percent change from baseline in modified Hidradenitis Suppurativa Score (mHSS).

HS-PGA response. HS-PGA response is defined as the achievement of at least a 2-point reduction in HS-PGA score compared to baseline.

DLQI response and absolute/percent DLQI total score change from baseline. DLQI response is defined as a decrease greater than 5.0 points from baseline in DLQI total score.

EQ-5D-3L Categories on Category questions and summary statistics on EQ - 5D -3L score questions.

Patient Global Impression of severity and change (PGI-s and PGI-c) categories.

Absolute and percent change from baseline in Work Productivity and Activity Impairment - Specific Health Problem (WPAI-SHP).

HS Symptom Diary items score change from baseline.

Objective(s)	Endpoint(s)

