**Table 2-7 Exploratory variables**

Variable	Type	Model	Missing data handling
HiSCR over time	exploratory	MELRM descriptive	use observed data only
Flare over time	exploratory	MELRM Kaplan Meier descriptive	use observed data only
AN count over time	exploratory	MMRM descriptive	use observed data only
AN50 over time	exploratory	MELRM descriptive	use observed data only
NRS30 over time	exploratory	MELRM descriptive	use observed data only
HiSCR25, HiSCR75, HiSCR90, HiSCR100 over time	exploratory	descriptive	use observed data only
AN25, AN50, AN75, AN90, AN100 AN 0/1, AN0/1/2 over time	exploratory	descriptive	use observed data only
No increase in draining fistulæ over time	exploratory	descriptive	use observed data only
No increase in abcesses over time	exploratory	descriptive	use observed data only
Inflammatory nodules, abcesses, draining fistulæ change from baseline over time	exploratory	descriptive	use observed data only
DLQI total score and component score over time	exploratory	descriptive	use observed data only
WPAI-HS over time	exploratory	descriptive	use observed data only
HS-dairy over time	exploratory	descriptive	use observed data only
PGI-s and PGI-c over time	exploratory	descriptive	use observed data only
EQ-5D	exploratory	descriptive	use observed data only

Following analyses will use the FAS.

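### SAP 2.13 specifies NRS30 over time on the FAS without the baseline NRS ≥ 3 condition of the Week 16 pain endpoint, which lowers the exploratory response rates

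*SAP*

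**What the plan says.** The secondary pain endpoint in SAP Table 1-1 is "Achievement of NRS30 at Week 16, among subjects with baseline NRS" of 3 or more. Protocol Table 2-1 and Section 12.5.1 agree. NRS30 itself is a fall from baseline that is both 30% or more and 2 units or more. The threshold of 3 is written as a condition on who is analysed, not as part of that responder rule.

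The long-term exploratory endpoint in the same SAP table is only "Achievement of pain relief as defined by NRS30", with no baseline condition.

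In SAP 2.13, the sentence after Table 2-7 reads "Following analyses will use the FAS". The Skin Pain/NRS30 text then says "The number and percentage of NRS30 responder subjects will be presented by visit" up to Week 52, adds figures of responder rates, and fits a mixed effects logistic model (MELRM) from Week 2 to Week 52 with fixed effects "treatment group, visit, baseline NRS score and the interaction between visit and treatment group". All of this is done for the study alone and for both studies pooled. Table 2-7 specifies observed data only.

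Three other SAP sections bear on the denominator:
- Section 2.1: summaries cover every subject in the population concerned unless something else is stated.
- Section 2.1.2: baseline pain is an average of up to 7 diary entries, and is missing if there are fewer than 4.
- Section 4: the only listed change from the protocol is the HS-PGA response definition.

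**The concern.** A responder rule that demands a 2-unit fall makes sense only in patients who have room to fall. The Week 16 endpoint deals with this through its baseline condition; the over-time analysis, as written, does not. Patients with little or no skin pain at entry then sit in the denominator at every visit and can contribute few or no responses, whatever the treatment does.

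Two things are at stake. The reported long-term pain response rates are too low as a description of patients who had pain to relieve. And the curve to Week 52 is drawn in a different population from the Week 16 endpoint that it appears to continue. Protocol 1.2 gives maintenance of efficacy at Week 52 as part of the study's purpose, so the curve is likely to be read as that continuation.

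**Working it through.** **1. Which denominator the text gives.** SAP 2.13 names the FAS. SAP 2.1 makes all subjects in the named population the default. The FAS definition (SAP 2.2) has no pain condition. Neither Skin Pain/NRS30, Table 2-7 nor the MELRM description (SAP 5.4.2.2) adds one. A patient without a baseline NRS has no change from baseline and drops out of an observed-data analysis. Read as written, the denominator is FAS patients with an observed baseline NRS and an observed value at the visit.

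**2. Who cannot respond.** For baseline b, response needs a fall of at least max(2, 0.3b).
- b < 2: the scale ends at 0, so a 2-unit fall is impossible.
- 2 ≤ b < 3: a 2-unit fall leaves b − 2, which is below 1. Response is possible only by becoming nearly pain-free.
- b = 3: a fall of 2/3 = 67%, to 1 or less, is needed.

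**3. The plan's own figure.** Inputs from Protocol 12.8.2 and SAP Section 3: 942 patients over two studies, three equal groups with placebo pooled, 80% qualified, 23% v 36%, two-sided alpha 4% (q2w) and 1% (q4w).
- n per group = 942/3 × 0.8 = 251.
- With the Fleiss continuity correction, the effective size is m = n(1 − 1/(nd))². For d = 0.13, m = 251 × (1 − 1/32.63)² = 235.9.
- Normal-approximation power at m is 85.4% for q2w and 70.0% for q4w. The stated figures are 85% and 70%, so they reproduce. Without the correction, n = 251 gives 87.5% and 73.4%.

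The planned pain rates therefore belong to the qualified 80%.

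**4. Effect on the rates.** Let q be the share of the denominator with baseline ≥ 3, r the response rate in that share, and s the rate below 3. The rate in the whole denominator is q·r + (1 − q)·s. With s = 0 it is q·r.

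| Assumption | From 36% | From 23% |
|---|---|---|
| q = 0.8, s = 0 (plan's share, worst case) | 0.8 × 36 = 28.8% | 0.8 × 23 = 18.4% |
| q = 0.7, s = 0 | 25.2% | 16.1% |
| q = 0.9, s = 0 | 32.4% | 20.7% |
| 80% qualified, 10% below 3 with s = 0, 10% without a baseline: q = 80/90 | 32.0% | 20.4% |
| q = 0.8, half of those below 3 respond at rate r: factor 0.8 + 0.1 = 0.9 | 32.4% | 20.7% |

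Only the 80% is the plan's figure; the other shares are assumptions to show the range. In the worst case at q = 0.8, the Week 16 active-to-placebo difference moves from 13 to 28.8 − 18.4 = 10.4 points, and the odds ratio from 1.88 to 1.79.

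**5. Patients involved.** 20% of 541 is about 108. Each secukinumab arm has about 541/3 = 180 patients, so 0.2 × 180 = 36. Each placebo-switch arm has about 541/6 = 90, so 0.2 × 90 = 18.

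**The case against.** The strongest reply is that the plan is silent rather than wrong. No sentence says that patients below 3 are included or counted as non-responders. The sample-size text, "Assuming 80% patients are qualified to calculate Pain variable NRS30", can be read as treating NRS30 as not calculable in the rest. SAP Section 1 says the data are analysed according to protocol Section 12, where the pain endpoint carries the condition. The separate Week 16 SAP, not among the documents, may hold the operational derivation. This lowers certainty about what will be programmed. It does not settle the denominator: the sample-size wording concerns the pooled Week 16 test, the protocol condition is attached to Week 16, and SAP 2.1 has a default that points to all FAS patients.

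A second reply is that 2.13 matches the exploratory endpoint row, which has no baseline condition. That is fair, and it means the absence of an entry in SAP Section 4 proves nothing. It does not make the unrestricted rate a sensible measure.

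Several stronger readings are tempting and not supported:
- **That everyone below 3 is unable to respond.** Only those below 2 are, and the documents do not give their share.
- **That literally the whole FAS is used.** Patients without a baseline drop out.
- **That the long-term treatment difference shrinks from 13 to 10.4 points.** That is a Week 16 upper bound. From Week 16 all patients receive secukinumab, so there is no placebo contrast afterwards.
- **That the restriction would make the Week 16 point match the confirmatory result.** The confirmatory analysis uses multiple imputation, pooled placebo and both studies combined, so the values would differ anyway.
- **That the MELRM is shown to be distorted.** Baseline NRS is already a covariate, and no calculation of any remaining effect is available.

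**Conclusion.** The point holds in this form: followed as written, the over-time NRS30 analyses include FAS patients with an observed baseline below 3, some of whom can never respond. Response rates are lowered by a factor of about 0.8 at worst, for example 36% to 28.8%. That bound assumes the plan's 80% qualified share, an observed baseline in all of the other 20%, and no responses among them. If some lack a baseline or respond, the factor is nearer 1.

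The consequence is limited to exploratory counts, figures and the MELRM, at study level and pooled. A reader might infer that the confirmatory pain claim is weakened. It is not: H7 and H8 are tested at Week 16 under the restricted endpoint. Some uncertainty remains because the Week 16 SAP could not be read.

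**What to change.** In SAP 2.13 (Skin Pain/NRS30) and in the NRS30 row of Table 2-7, state that all NRS30 over-time analyses (counts, rates, figures and MELRM, study-level and pooled) are in FAS subjects with baseline NRS ≥ 3, and report that denominator by group and visit. Keep the whole FAS for skin pain on the original scale (SAP 2.11, Additional endpoints), so that patients with low baseline pain are still described.

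The cost is one sentence and a population flag that the Week 16 endpoint already needs. The downside is a smaller denominator, the same one already accepted for the secondary endpoint.
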